Patients will be removed from the study for any of the following reasons: death or patient withdrawal. The protocol director may also withdraw a patient from the study for one or more of the following reasons: failure of the patient to follow the instructions of the protocol study staff, the protocol director decides that continuing participation could be harmful to the patient, pregnancy (if applicable), the patient needs treatment not allowed in the study, the study is cancelled, other administrative reasons, or unanticipated circumstances. Patients that have been removed from or discontinue the study will be followed for survival information until death.

Alternatives

Alternative therapies include chemotherapy alone, standard chemotherapy/radiation, upfront resection of pancreas tumor, palliative symptomatic relief, or no further treatment. Additionally, patients may choose to receive treatment to improve quality of life but that may have no effect on the growth of their cancer. The risks of chemotherapy and standard chemotherapy/radiation include nausea, vomiting, diarrhea, fatigue, bone marrow suppression, and sepsis. The potential benefits of chemotherapy or standard chemotherapy/radiation are prolonged survival. The risk of pursuing no further treatment is tumor progression or spread.

VII. COMPENSATION

Subjects will not be paid to participate in the study.

VIII. ADVERSE EVENTS: LIST AND REPORTING REQUIREMENTS

Adverse Events and Potential Risks List

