- The primary endpoint is the rate of acute (within 3 months of treatment) G3+ gastrointestinal toxicities as assessed by CTCAE v4.0.

Study Design and Decision Rules

The purpose of this study is to demonstrate the feasibility of conducting a study assessing the proposed regimen. The sample size of twenty patients with confirmed resectable or borderline resectable pancreas cancer is selected based on financial and logistic considerations. However, we still propose decision rules based on testable hypotheses whenever possible. If, at the conclusion of the trial, none of the following stopping rules has been crossed, we will conclude that the proposed regimen and trial design warrants further phase II study for assessing SBRT followed by surgery in this disease population.

Accrual stopping rules

If, 4 months following the date IRB approval is obtained, no patients have been accrued, we will conclude the study does not demonstrate sufficient feasibility. Thereafter, the accrual rate will be monitored bi-monthly. If at any evaluation time point, the accrual rate is less than 0.5 per month, we will conclude the study does not demonstrate sufficient feasibility.

Toxicity Stopping Rules

The toxicity feasibility stopping rules are specified as the following:

- The toxicity rate is defined as the proportion of treated patients with resectable and/or borderline resectable pancreas cancer who experience at least one grade 3+ adverse event, and is considered at least possibly related to the preoperative treatment (i.e. an adverse event with attribute specified as “possibly,” “probably,” or “definitely” related to SBRT). The toxicity rate will be evaluated when the first 10, the first 15 and then 20 patients are enrolled and the toxicity data are available.
 - When toxicity data are available on the first 10 evaluable patients, if the toxicity rate is greater than 0.54 (> 5 patients experienced defined AEs), we will conclude the study does not demonstrate sufficient feasibility. Otherwise, continue accrual.
 - When toxicity data are available on the first 15 evaluable patients, if the toxicity rate is greater than 0.46 (> 6 patients experience defined AEs), we will conclude the study does not demonstrate sufficient feasibility. Otherwise, continue accrual.

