 - When toxicity data are available on all 20 evaluable patients, if the toxicity rate is greater than 0.42 (>8 patients experience defined AEs), we will conclude the study does not demonstrate sufficient feasibility.
 - This decision rule based on a sample size of 20 patients will have more than 80% chance to conclude the study does not demonstrate sufficient feasibility if the toxicity rate is $\geq 50\%$ and only have less than 17% chance to conclude the study does not demonstrate sufficient feasibility if the toxicity rate is $\leq 30\%$.
 - If 4 or more patients in the first 10, or after 10 patients, 40% or more treated patients experience treatment delay (> 4 weeks), we will conclude the study does not demonstrate sufficient feasibility.

Completion of Therapy Stopping Rules

The completion of therapy stopping rules are specified as the following:

- If at least 6 patients among 20 evaluable patients complete all preoperative and operative therapy including R0 or R1 resection, we will conclude the study warrants further phase II study, provided that none of the other feasibility stopping rules are crossed at any time.
- If 5 or less than 5 patients among 20 evaluable patients complete all preoperative and operative therapy we will conclude that the study does not demonstrate sufficient feasibility.
 - This decision rule based on a sample size of 20 patients will have more than 80% chance to conclude the study does not demonstrate sufficient feasibility if the R0/R1 resection rate is $\leq 20\%$ and only have less than 13% chance to conclude the study does not demonstrate sufficient feasibility if the R0/R1 resection rate is $\geq 40\%$.

Analysis Plan

All acute AE (within 3 months after treatment) and the maximum grade for each type of adverse events (including all adverse events and those that are possibly, probably or definitely related to study treatments) will be recorded for each patient. The frequency tables will be reviewed to determine the patterns. Point estimate and confidence interval will be reported for binary endpoints.

Supplementary Analysis Plans (Secondary Endpoints)

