All late AE and the maximum grade for each type of adverse events (including all adverse events and those that are possibly, probably or definitely related to study treatments) will be recorded for each patient. The frequency tables will be reviewed to determine the patterns. Point estimate and confidence interval will be reported for binary endpoints. All patients meeting the eligibility criteria and confirmed by central review who have signed a consent form and have begun any dose of treatment will be evaluable for the following secondary endpoints, unless otherwise specified.

- The positive margin resection rate is defined as number of patients achieved R0 versus R1/R2 resection during surgery divided by number of evaluable patients. (R0= negative margin, R1= microscopically positive margin, R2= macroscopically positive margin). Point estimate and confidence interval of the rate will be reported.
- The histopathologic response rate is defined as number of patients achieved CR or PR determined according to histopathologic examination during pre-operative chemo or chemoradiotherapy divided by number of evaluable patients. Point estimate and confidence interval of the rate will be reported.
- Time to locoregional recurrence is defined as time from the date of registration to the date of the first documented locoregional recurrence. The Kaplan-Meier methods will be used to estimate the median time, and event-free rate at specific time points (6 month, 12 month, etc.).
- Time to distant recurrence is defined as time from the date of registration to the date of the first documented distant recurrence. The Kaplan-Meier methods will be used to estimate the median time, and event-free rate at specific time points (6 month, 12 month, etc.).
- Overall survival is defined as time from the date of registration to the date of the death due to all causes. The Kaplan-Meier methods will be used to estimate the median time, and event-free rate at specific time points (6 month, 12 month, etc.).

Safety Stopping Rules

In addition to toxicity feasibility stopping rules, accrual will be temporarily suspended to the study, if at any time, we observe events considered at least possibly related to study treatment an adverse event with attribute specified as ("possible," "probably," or "definite") that meet the following:

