Patients will be evaluated for anti-tumor effect by follow-up imaging (pancreas protocol CT and/or PET-CT imaging) as outlined above. All subsequent scans (post-treatment) will be compared to the same pretreatment CT that was used in conjunction with radiation treatment planning.

Patients will be evaluable for toxicity and evaluable for objective response at the follow-up intervals specified above.

Disease Parameters

Pancreatic tumor response will be based upon standard radiographic criteria for the treated lesion and will be prospectively recorded in the UC secure database. Radiographic response of the pancreatic tumor by diagnostic CT scans will be defined according to RECIST criteria as described below:

- CR = complete disappearance of index lesion
- PR = at least 30% decrease in the longest diameter of the index lesion
- PD = more than 20% increase in the longest diameter of the index lesion
- SD = does not meet criteria for PR or PD

Local tumor progression will be defined as $\geq20\%$ increased size on CT scan compared to a CT

scan from prior to treatment. Distant progression will be defined as any new tumor found outside of the pancreas or periampullary region on CT scan. Local and/or distant progression will be evaluated by both PET/CT (if available) and CT scan as deemed by treating physician.

Methods for Evaluation of Measurable Disease

Pancreas protocol CT scans (biphasic imaging, 1.25 mm cuts) and/or FDG PET-CT scans (optional and if recommended by the treating physician) will be obtained at all follow-up intervals as described in the treatment calendar.

XIII. RESPONSE CRITERIA

Evaluation of Target Lesions

Patients' responses to therapy will also be evaluated clinically after completion of their Linac based SBRT. The following are clinical definitions for response:

- CR = complete alleviation of pain or other symptoms thought to be related to the index lesion
- PR = improvement, but not complete elimination, of pain or other symptoms thought to be related to the index lesion
- PD = worsening of pain or other symptoms thought to be related to the index lesion SD = does not meet criteria for PR or PD
- Radiographic response will be defined as outlined in section 11.1.2.

Evaluation of Non-Target Lesions

Standard radiographic criteria will be utilized for non-target lesions. Any disease outside of the pancreas region will be considered metastatic disease. If possible a biopsy should be obtained to confirm metastasis.

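### Survival is the only follow-up named for patients removed from the study, so grade 3+ events after removal and late toxicity can be missed

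*Combined protocol and SAP*

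**What the plan says.** **Removal and later follow-up.** Section VI, Criteria for Removal from Study, lists grounds on which a patient may be withdrawn. One is that "the protocol director decides that continuing participation could be harmful to the patient"; another is a need for treatment that the study does not allow. The paragraph ends: "Patients that have been removed from or discontinue the study will be followed for survival information until death". Duration of Follow Up, in the same section, gives near-identical survival wording for patients who have completed five years, that is, once the scheduled visits are over.

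**What depends on toxicity follow-up.** The primary endpoint in Section IX is the "rate of acute (within 3 months of treatment) G3+ gastrointestinal toxicities as assessed by CTCAE v4.0". Late gastrointestinal toxicity, beyond 3 months, is a secondary objective. The Toxicity Stopping Rules act on related grade 3+ events.

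**Who is counted.** The stopping-rule section begins: "The toxicity rate is defined as the proportion of treated patients". The looks themselves use another term: "When toxicity data are available on the first 10 evaluable patients" and, at the end, "When toxicity data are available on all 20 evaluable patients". Section IX explains *evaluable* only for a list of secondary endpoints: eligible, consented patients who "have begun any dose of treatment will be evaluable for the following secondary endpoints, unless otherwise specified". Section XII adds: "Patients will be evaluable for toxicity and evaluable for objective response at the follow-up intervals specified above".

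**Text pointing the other way.** The Analysis Plan and the Supplementary Analysis Plans in Section IX say that acute and late adverse events are recorded for every patient. Section X (Data Entry and Compilation) captures toxicities reported with radiotherapy, and the date and reason of any withdrawal.

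**The concern.** The trial has at most 20 patients, and toxicity is its primary endpoint. If the removal paragraph is followed as written, adverse-event visits stop when a patient is removed and only vital status is pursued. Removal on grounds of possible harm is plausibly related to later toxicity, so the missing follow-up would not be a random sample. A patient with a grade 2 event or an emerging problem could be taken off study and reach grade 3 a few weeks later, still inside the 3-month window, without the event being collected.

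Three results are exposed: the acute grade 3+ gastrointestinal rate, the stopping rule built on related grade 3+ events, and the late-toxicity rate. Late toxicity is the most exposed, because a patient removed early contributes nothing to it. The plan also does not say whether a removed patient counts as event-free at a look, is excluded, or is replaced.

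**Working it through.** **1. The texts side by side.**

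| Place | What it gives | Removed patients covered? |
|---|---|---|
| Section VI, Criteria for Removal | Survival follow-up | Yes, explicitly; adverse events not mentioned |
| Section IX, Analysis Plan and Supplementary Analysis Plans | Acute and late events recorded for every patient | Not mentioned |
| Section IX, definition of the toxicity rate | Treated patients | In the denominator by implication |
| Section IX, the three looks | Evaluable patients, not defined for toxicity | Unclear |
| Section XII | Toxicity evaluable at follow-up visits | Not if they no longer attend |

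The only sentence about removed patients names survival alone. The general sentences conflict with it but do not say that it yields to them.

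**2. What can be lost.** The stopping rule counts patients with at least one related grade 3+ event.
- Removed because of a grade 3+ event: already counted, nothing lost from the acute rate.
- Removed at grade 2 or for emerging risk, reaching grade 3+ later but within 3 months: lost from the acute rate.
- Grade 3 before removal, grade 4 after it: the rate is unchanged, but the maximum-grade table is wrong.
- Any event beyond 3 months: lost from the late rate.

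**3. The plan's own figures first.** Inputs from Toxicity Stopping Rules: stop if more than 5 of 10, more than 6 of 15, or more than 8 of 20. With true rate p, carry the binomial distribution of the event count from look to look, remove the probability above the limit at each look, and add the removed parts:
- p = 0.50: 0.3770 + 0.3258 + 0.0917 = 0.794 (the plan states more than 80%).
- p = 0.30: 0.0473 + 0.0900 + 0.0299 = 0.167 (the plan states less than 17%).

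The second figure is reproduced; the first falls just short.

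**4. Effect of unseen events.** The documents give no removal rate. *Assumption:* a share m of the patients with a qualifying event is removed before that event is seen. Take p = 0.50, the rate at which the plan states its chance of stopping.
- Counted as event-free: observed rate = p(1 − m).
- Dropped and replaced: observed rate = p(1 − m) / (1 − pm).

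| m | Event-free: observed rate | Chance of stopping | Replaced: observed rate | Chance of stopping |
|---|---|---|---|---|
| 0 | 0.500 | 79.4% | 0.500 | 79.4% |
| 5% | 0.475 | 72.7% | 0.487 | 76.1% |
| 10% | 0.450 | 65.0% | 0.474 | 72.3% |
| 20% | 0.400 | 47.9% | 0.444 | 63.2% |
| 30% | 0.350 | 30.8% | 0.412 | 52.1% |

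In patients, m = 10% is 20 × 0.50 × 0.10 = 1 expected patient of 20, and m = 20% is 2.

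**5. One patient at the last look.** Nine events in 20 is 0.45, and the rule stops. With one of the nine unseen and counted event-free, 8/20 = 0.40 and it does not. With that patient excluded, 8/19 = 0.421, which exceeds the stated rate limit of 0.42 but not the stated count limit of 8, so the two forms of the rule disagree.

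**The case against.** A reader might infer that the patients most prone to toxicity leave the toxicity data altogether. The documents do not support that. The rate needs only one grade 3+ event per patient, so a patient removed for such an event has already contributed it. Toxicities reported with radiotherapy are entered in the database, and no text discards data collected before removal.

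A reader might also infer that adverse-event collection is expressly ended, or that irradiated patients are left without safety surveillance. Neither is stated. Section IX speaks of every patient, Section IV has all patients monitored clinically after SBRT, and Section VIII requires reporting of all fatal events, and of other serious unanticipated events, once the principal investigator learns of them, with no limit to patients still on study.

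Three further points are fair. Stopping SBRT early is not itself removal: the protocol director may withdraw a patient but need not, and harm is one of several grounds. The toxicity rate is already defined over treated patients. And 50% is a rate the rule is meant to detect, not what the protocol expects. Section VI puts obstruction, perforation or hemorrhage below 5% with standard radiotherapy and expects a comparable rate here, although that is narrower than any grade 3+ event.

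These points limit the likely size of the problem but do not close the gap. Section VI gives a specific rule for removed patients, and the general wording elsewhere makes the document inconsistent without overriding that rule. Relying on the investigator to hear of an event is not the same as scheduled ascertainment of a primary endpoint.

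**Conclusion.** The concern holds in a limited form. Survival is the only follow-up named after removal, one ground for removal is plausibly linked to toxicity, and no text says how a removed patient counts at the looks. The possible loss is confined to grade 3+ toxicity that first appears, or worsens, after removal within the 3-month window, and to late toxicity. Where removal is related to harm, both rates would be biased downward.

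The size cannot be known from the documents. Under assumed losses of 10% or 20% of patients with events, at a true rate of 50%, the chance of stopping drops by 14.4 or 31.5 percentage points if they are counted event-free, and by 7.1 or 16.2 points if they are dropped and replaced. These figures illustrate sensitivity and do not forecast a loss. The change is worth making because one patient can decide the last look and the correction is cheap.

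**What to change.** 1. **Section VI, Criteria for Removal from Study.** Amend the last sentence so that every patient who received at least one SBRT fraction continues adverse-event collection after removal or discontinuation, on the same schedule as other patients and in addition to survival, unless consent to follow-up is withdrawn.
2. **Cover the whole acute window.** Add an adverse-event contact or record review that reaches the end of 3 months. Appendix I has visits at 4–6 weeks and 4 months but no 3-month column, while Section IV lists a 3-month visit; the two should be reconciled. Late collection should follow the calendar, which runs adverse-event evaluation through years 2–5, so that removed patients are not handled differently.
3. **Section IX, Toxicity Stopping Rules.** At the 10, 15 and 20 patient looks, replace *evaluable* with all patients who received at least one fraction, in line with the treated-patient definition above them.
4. **Reporting.** State how many treated patients lack complete 3-month follow-up, and add a sensitivity analysis that counts them as events.

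The cost is a few sentences and the effort of obtaining records for a small number of patients followed elsewhere. Appendix I, footnote 3, already requires records from local centers for scheduled evaluations, though it does not mention removed patients. Clinical management does not change.

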not the PI believes the event to be related to the study. All other events, which are both serious and unanticipated, must be reported to the UC IRB within a time period as specified by current institutional guidelines after the PI learns of the event. Events which are serious, but anticipated, should be reported as part of the continuing review application. If any of these Serious Adverse Events requires a change to the protocol or consent form, the PI must make those changes promptly and submit the revised documents to the UC IRB. Important Adverse Events that are unanticipated must be reported to the UC IRB within a time period as specified by current institutional guidelines. If the Important Adverse Event requires changes to the protocol or consent form, the PI must make those changes promptly and submit the revised documents to the UC IRB. All other unanticipated Adverse Events or changes to the protocol and consent form must be reported to the UC IRB, within a time period as specified by current institutional guidelines.

IX. STATISTICAL CONSIDERATIONS

Study Overview

This pilot study is designed to assess the feasibility of giving neoadjuvant SBRT in resectable and/or borderline resectable pancreas cancer patients. The feasibility demonstration will establish the infrastructure for future randomized phase II clinical trials in a single or multi-center setting. Twenty patients with resectable and/or borderline resectable pancreas cancer, confirmed by multi-disciplinary radiologic review, will be enrolled and treated. The decision regarding whether this study demonstrates sufficient feasibility to support a phase II study testing novel regimens in this disease population will be based on three key considerations:

- The study can meet the accrual goal.
- The proposed preoperative SBRT will result in no more toxicity than has been established previously in the borderline resectable and locally advanced setting by evaluating the prevalence of grade 3+ toxicities and treatment delay rate (> 4 weeks).
- The completion rate of preoperative and operative therapy meets the goals.

Sample Size

A maximum of 20 patients will be enrolled if the trial completes accrual.

Accrual time

The anticipated monthly accrual rate is approximately 1-2 patients per month. The trial is expected to accrue in approximately 24 months.

Statistical Design for Primary Endpoints

Primary Endpoints

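### The toxicity consideration for going to phase II is a comparison with earlier experience, but the grade 3+ rule has no stated comparator, so not crossing it cannot show that SBRT is no more toxic than before

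*Combined protocol and SAP*

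**What the plan says.** Section IX, Study Overview, lists three considerations for deciding whether the trial supports a phase II study. The second is that preoperative SBRT "will result in no more toxicity than has been established previously in the borderline resectable and locally advanced setting", to be judged "by evaluating the prevalence of grade 3+ toxicities and treatment delay rate (> 4 weeks").

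Under Study Design and Decision Rules, the operative conclusion is that if "none of the following stopping rules has been crossed, we will conclude that the proposed regimen and trial design warrants further phase II study". The same paragraph says that the 20 patients were chosen on financial and logistic grounds, with decision rules built on testable hypotheses where possible.

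Under Toxicity Stopping Rules, the counted patients are those "who experience at least one grade 3+ adverse event, and is considered at least possibly related to the preoperative treatment". The event is not restricted to one organ system. There are looks at 10, 15 and 20 patients, and the study is judged not feasible if more than 5, more than 6 or more than 8 patients have the event. The last limit reads "if the toxicity rate is greater than 0.42 (>8 patients experience defined AEs"). The rule "will have more than 80% chance to conclude the study does not demonstrate sufficient feasibility if the toxicity rate is" 50% or higher, and a chance below 17% of doing so if the rate is 30% or lower. Treatment delay has its own limit: 4 or more of the first 10 patients, and after that "40% or more treated patients experience treatment delay (> 4 weeks").

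**The concern.** The second consideration is comparative: it asks for toxicity no greater than a level already established. A comparison needs a reference value, and Section IX gives none. The only rates attached to the grade 3+ rule are 30% and 50%, and neither is traced to earlier patients.

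Because the trial proceeds to a phase II recommendation when no rule is crossed, a reader of the results could take an uncrossed grade 3+ rule as meeting the second consideration as worded. What is at stake is that inference. The probability that the rule is passed at rates of 30% to 40% shows how little a pass says about equality with any earlier rate. The stated chance of flagging a 50% rate also needs checking, since it describes what the rule can do.

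**Working it through.** **Is a comparator stated anywhere?** The documents report these grade 3 or higher figures for earlier patients:

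| Source in the protocol | Figure | Event and population |
|---|---|---|
| III. Rationale, multi-institutional 6.6 Gy x 5 study | none seen | GI, acute and late; 70 locally advanced or borderline patients |
| III. Rationale, single-fraction 25 Gy phase II study | 2/15 = 13% | GI; patients alive more than 6 months after SBRT |
| III. Rationale, neoadjuvant proton 5 Gy x 5 series | 4/15 = 26.7% (grade 3) | Not limited to GI; different modality |

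None is cited as the basis for 30% or 50%. None matches the rule's event (any organ, at least possibly related to SBRT) in a like population and treatment.

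**Inputs for the rule** (IX, Toxicity Stopping Rules). Looks at n = 10, 15, 20; flag if the cumulative count X exceeds 5, 6, 8. The printed rate limits agree with these counts: 0.54 x 10 = 5.4, 0.46 x 15 = 6.9, 0.42 x 20 = 8.4. I assume independent patients with a common true rate p and complete data at each look.

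**Formula.**

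P(flag) = P(X10 > 5) + P(X10 ≤ 5, X15 > 6) + P(X10 ≤ 5, X15 ≤ 6, X20 > 8)

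Here X10 is Binomial(10, p), and each later block of 5 patients adds an independent Binomial(5, p). P(pass) = 1 − P(flag).

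**The plan's own figures first.**

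- p = 0.30: 0.0473 + 0.0900 + 0.0299 = 0.1672. Stated as less than 17%; correct.
- p = 0.50: 0.3770 + 0.3258 + 0.0917 = 0.7944 (terms rounded). Stated as more than 80%; the exact value is 79.4%, which is 0.6 points short.
- Check at p = 0.50 by counting: of 2^20 = 1,048,576 equally likely outcome sequences, 215,545 pass. 215,545 / 1,048,576 = 0.2056, and 1 − 0.2056 = 0.7944.
- P(flag) reaches 80% at p = 0.5023.
- A single look at 20 patients would give 74.8% at p = 0.50 and 11.3% at p = 0.30, so that reading does not recover the stated figure.

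**Pass probability by true rate of the counted event.**

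| True rate | P(flag) | P(pass) |
|---|---|---|
| 26.7% | 9.9% | 90.1% |
| 30% | 16.7% | 83.3% |
| 35% | 30.9% | 69.2% |
| 40% | 47.9% | 52.1% |
| 45% | 65.0% | 35.0% |
| 50% | 79.4% | 20.6% |

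**What a passing result can look like.** The path 5/10, 6/15, 8/20 crosses no limit. The exact (Clopper-Pearson) 95% interval for 8/20 is 19.1% to 63.9%. The upper limits for 7/20 and 6/20 are 59.2% and 54.3%. All three of these passing counts are compatible with a rate of 50%.

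**The case against.** The best defence is that this is a 20-patient pilot. The protocol says openly that its size was set by money and logistics, and wide pass probabilities largely follow from 20 patients. The plan lists considerations, and its operative sentence concludes only that phase II is warranted; nowhere does it write that a pass proves equal toxicity. Other protections also run: the treatment-delay limit, suspension of accrual for treatment-related deaths, review of grade IV and V events judged unrelated, and oversight by a DSMB. The shortfall from 80% is 0.6 points and disappears at a true rate of 50.2%.

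Most of this stands. It is why no larger sample or new limit is asked for, and why the 80% figure is a minor correction. It does not supply a reference rate. The consideration is still worded as a comparison, it feeds the phase II decision, and the death rule and DSMB do not say what rate was established before.

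Three stronger readings are tempting and are not supported:

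- **That 30% and 50% are too lenient because earlier SBRT series saw 0% or 13%.** Those figures are GI-only, while the rule counts any organ. The proton series, not limited to GI, reported 26.7%, close to 30%. The documents do not permit a like-for-like ranking either way.
- **That a pass at least rules out 50%.** A true 50% passes about one time in five, and passing counts of 6, 7 or 8 of 20 have intervals that include 50%.
- **That the rule is wrong because its event differs from the primary endpoint** (acute grade 3+ GI toxicity, with no attribution condition). The two are defined under separate headings, and the Analysis Plan records events both ways: "including all adverse events and those that are possibly, probably or definitely related to study treatments". The rule's time window is unstated and could be clarified, but that is missing detail and not part of this point.

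**Conclusion.** The point holds in a limited form. The second phase II consideration has no stated comparator, and the grade 3+ rule cannot provide one: it passes with probability 90% at 26.7%, 83% at 30%, 52% at 40% and 21% at 50%. Not crossing it does not show toxicity no greater than established. The wording should be corrected because it bears on what the trial may conclude; the design and limits are not shown to be wrong. The misstated operating figure (79.4% against more than 80%) changes no decision.

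The probabilities concern the grade 3+ rule alone; a favourable overall conclusion also needs the accrual, delay and completion rules uncrossed. They rest on independent patients, a common rate, and toxicity data complete at each look.

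**What to change.** 1. In Section IX, Study Overview, reword the second consideration in one of two ways.
   - Describe the grade 3+ rule as a feasibility screen that flags a true SBRT-related grade 3+ rate of 50% with probability about 79% and a rate of 30% with probability about 17%. Give the pass probabilities (83% at 30%, 52% at 40%, 21% at 50%). Do not describe a pass as showing no more toxicity than before, or as excluding 50%.
   - Or keep the comparison, and state the prior rate, its event definition and source, and the rule's pass probability at that rate.
2. Minor: in Toxicity Stopping Rules, restate the chance of flagging a true rate of 50% as about 79%. The figure at 30% needs no change.

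Both are text changes in Section IX. They need no extra patients, visits or data, and the existing limits can stay. The cost is a slightly less favourable stated claim and operating figure.
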